Aims 1-4	Medical cannabis use	Initial soft-gel capsule dispensed at Vireo Certification for medical cannabis (date, doctor, conditions) All medical cannabis products dispensed (date, product, dose, amount dispensed) Self-reported medical and unregulated cannabis use (product, # of days used, route, dollar amount of unregulated cannabis purchased, ASI)	PR MR PR TQ
Primary outcome variables			
Aims 1, 4	Pain Severity	Brief Pain Inventory (BPI) Severity subscale ⁹⁰	TQ
Secondary outcome variable			
Aims 2, 4	Inflammatory cytokines	Pro-inflammatory cytokines (TNF α , IL-6) Anti-inflammatory cytokines (IL-4, IL-10)	B B
Aims 3, 4	Adverse events	VL, CD4 count AIDS Clinical Trial Group (ACTG Adherence) ⁹³ , Visual Analog Scale (VAS) ⁹⁴ ARVs dispensed Depression (Center for Epidemiological Studies-Depression Scale [CES-D])), Generalized Anxiety Disorder (GAD-7) ⁹⁶	B IQ PR IQ
Other measures			
Aims 1-4	Sociodemographics	Age, race/ethnicity, education, insurance, sex, gender	IQ
Aims 1-4	Pain characteristics	Brief Pain Inventory (BPI) Interference subscale ⁹⁰ Pain catastrophizing scale ⁹⁸ , Pain DETECT questionnaire ⁸⁴	IQ IQ
Aims 1-4	Pain treatment	Pain treatment (SSRIs, gabapentin, injections, physical therapy)	IQ/MR/PR
Aim 3	Substance use/disorder	Smoking (Fagerstrom test for nicotine dependence) ⁹⁹ , Alcohol Use Disorders Identification Test (AUDIT) ¹⁰⁰ , ASI ⁹⁷	IQ
Aim 3	HIV Risk Behaviors	HIV risk behaviors (HIV Risk-taking Behavior Scale ¹⁰¹⁻¹⁰³)	IQ
Aims 3, 4	Psychiatric symptoms	PTSD Checklist (PCL), ¹⁰⁴ Insomnia severity index, ¹⁰⁵	IQ
Aims 1, 3, 4	Quality of Life	Roland Morris Disability Questionnaire ¹⁰⁶ , Patient Reported Outcomes Quality of Life-HIV (PROQOL-HIV) ¹⁰⁷	IQ
Aims 1-4	Medical comorbidities	Comorbidities (obesity, cardiovascular disease, diabetes)	MR
Aims 1-4	Side effect vs benefit	Treatment Satisfaction Questionnaire for Medication (TSQM-9) ⁹¹	TQ
Aims 1-4	Urine cannabinoid	Urine GCMS for cannabinoids	

B=blood test; MR=Medical records; PR=Pharmacy records or Prescription Monitoring Program; IQ= in-person questionnaire; TQ=phone questionnaire; SSRI=selective serotonin reuptake inhibitor; TQ measures occur every week; IQ occurs at 0 and 14 weeks. B occurs at 0 at 14 weeks.

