Other key outcome variables will be alternative pain measures (painDETECT,⁸⁴ pain catastrophizing⁹⁸).

Other measures that have strong associations with medical cannabis use or neurologic pain will be measured, including biological sex, substance use, quality of life, HIV risk behaviors, symptoms of post-traumatic stress disorder (PTSD), insomnia and medical comorbidities (Table 8).

3) Study Population

3.A. Sample size and power

determination. For our primary analysis (Aim 1), we based our power analysis on proportion of participants with clinically significant change in BPI pain severity scale (30% reduction) in each condition.^{8,48} We will recruit 100 participants in total; we anticipate that approximately 50 will use high THC soft gel

capsules and 50 will use high CBD soft gel capsules. Conservatively assuming 15% attrition in each arm, 42 participants will be in each arm. Because the individual-level intra-class correlation coefficient (ICC) associated with change in pain severity over time is unknown, we conducted simulation studies with varying ICC values, i.e., 0.2, 0.3, and 0.4. We present power calculations for pain severity in Table 9. Based on prior studies,^{47,48} we predict that 40% of those using high THC capsules will experience clinically significant reduction in pain and 20% of those using high CBD capsules will experience clinically significant reduction in pain.¹¹⁰ We will have 84% power at a significance level of 5% (two-tailed test) to detect a 20% difference in proportion of participants who achieve clinically significant reduction in pain during the follow-up period between high THC soft-gel capsules (40%) and high CBD (20%) soft gel capsules. We will have greater power to detect a larger difference or when ICC is lower.

For analyses with continuous dependent variables (Aim 2-3), a sample size of 42 participants/arm will allow us to have >90% power to detect a moderate effect size (i.e., Cohen's $d=0.5$) under a more stringent condition (ICC=0.4). We will have greater power when the effect size is larger or when ICC is lower.

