4. Study records will be kept in locked files and/or within limited access, code-protected computer files, available only to the investigators and study personnel.
5. Publication or presentation of study results will not identify subjects by name.

In addition to addressing issues of confidentiality, it is crucial that we protect participants from emotional distress that may occur during research visits. All visits will occur in medical facilities. If emotional distress occurs during research visits an on-site physician will assess the patient. Per clinical judgment, the participant will either be referred to the Emergency Room or to their treating physicians the following day.

6.C. Potential benefits.

Neuropathic pain in PLWH is associated with poor HIV outcomes, including poor ARV adherence,³² virologic failure,³³ and poor retention in care.^{19,33} PLWH experience a high burden of pain,⁴⁻¹¹ and most commonly experience neuropathic pain.^{12,13} Medical cannabis has known analgesic properties in PLWH with neuropathic pain.^{24,25} Participants in our study will have been evaluated by their own physicians and deemed to be appropriate to receive medical cannabis based on those standards already. By participating in this study, they may experience benefit from medical cannabis use by experiencing improved pain. They may experience increased attention from research staff during the study period, resulting in improved pain, psychological, and HIV outcomes.

7) Data Analysis

7.A Data Analyses: *Intention-to-treat principle* will be used in primary analyses. If key variables (age, sex, medical comorbidities) are unequal among arms, we will conduct adjusted analyses. We will also conduct per-protocol analyses; medical cannabis use for at least 3 months of products will represent sufficient study participation.

Missing data: We will conduct multiple imputations using Markov Chain Monte Carlo imputation methods. Results from multiple imputed data sets will be pooled into a single dataset. We will compare statistical results using datasets with imputed values and the dataset that drops missing values.

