Aim 1: Examine how medical cannabis use affects self-reported pain. H1: The effect of medical cannabis use on self-reported pain-severity will differ by THC/CBD content. The primary outcome will be change in BPI pain severity scale (ordinal variable, 0-10; measured at baseline and weekly for 14 weeks). A clinically significant change is 30% reduction in BPI pain severity scale.⁹² Secondary measures will include BPI pain interference scale and neuropathic pain (painDETECT). We will compare the proportion of participants who achieve clinically significant change in pain at 14 weeks between those who use high THC soft gel capsules and those who use high CBD soft gel capsules. BPI pain interference scale and painDETECT will be compared between those using high THC vs high CBD as well. We will use mixed-effects logistic regression to test the effect of study arm on pain relief across the course of the study. Results will be adjusted for covariates associated with the outcomes of interest on bivariate testing. We will repeat this model using alternative measures of medical cannabis (cumulative dose of THC and CBD).

Aim 2: Examine how medical cannabis use affects pro- and anti-inflammatory cytokines. H2: Medical cannabis that has higher THC content will have greater reduction in pro-inflammatory

cytokines ($TNF\alpha$, $IL-6$). *H3: Medical cannabis that has higher CBD content will have greater increase in anti-inflammatory cytokines ($IL-4$, $IL-10$).* We will examine how pro- and anti-inflammatory cytokines measured at 0 and 14 weeks change in participants using high THC products versus high CBD products. We will use mixed-effects linear regression analyses to examine intervention and time effects as well as intervention-by-time interactions. This approach is appropriate in the event that the pro- and anti-inflammatory cytokine data show a non-normal distribution. We will repeat this model using alternative measures of medical cannabis (cumulative dose of THC and CBD). We will adjust for other chronic conditions that may lead to change in inflammatory cytokines, such as obesity, cardiovascular disease, and diabetes.

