Aim 3: Examine how medical cannabis use affects adverse events. *H4: Participants who use high THC (vs. high CBD) cannabis products will have more psychological symptoms, poorer ARV adherence, and less suppressed VL.* We will examine whether participants using high THC products vs high CBD products have a greater chance of adverse events, including psychological symptoms, ARV adherence, and VL. We will use mixed-effects linear regression analysis for continuous measures (VL, ARV adherence, and psychological symptoms). Each adverse event (Table 8) will be included in a separate model. We will repeat this model using alternative measures of medical cannabis (cumulative dose of THC and CBD).

Aim 4: Explore mechanisms by which medical cannabis promotes analgesia. *H5: Different doses of THC and CBD will have differing effects on inflammatory cytokines, psychological symptoms, and ultimately analgesia.*

We will use a pooled analysis of THC and CBD, using weekly questionnaires and PMP records. We will examine these relationships longitudinally in a stepwise process. First, we will conduct a mixed-effects model to examine how potential mediators lead to analgesia (reduction in BPI severity score). We will repeat analyses for possible mediators, including inflammatory cytokines and psychological symptoms. We will also determine if exposures influence changes in these variables over time, which in turn, influence change in analgesia (e.g., using time-lagged mediators and outcomes). Mediators found to be significant will be included in the final model.⁹² We will calculate the standardized total effect from the exposures to analgesia as well as the standardized mediational (i.e., indirect) effects via mediators. The mediational effect is calculated as the product of the effect from the exposures to the mediators, and the effect from the mediators to the outcome.

8) Data quality control and database management

Data management: Questionnaire, medical records, and PMP data will be de-identified and entered by study staff into a password-protected computer and database. Paper records will be stored in a locked filing cabinet that only research staff can access. Medical and PMP record data will be de-identified and entered in a secure HIPAA compliant web-based system. To protect confidentiality, we will use separate processes for ID- and name-based files and seek a certificate of confidentiality.

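### The missing-data rule pools the imputed data into one dataset and gives no rule for combining variances; read literally, it makes Aim 2 arm-by-time standard errors about 10-15% too small

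*Combined protocol and SAP*

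**What the plan says.** The missing-data paragraph of Section 7.A has three sentences. The first sets the method: "We will conduct multiple imputations using Markov Chain Monte Carlo imputation methods". The second says what happens to the output: "Results from multiple imputed data sets will be pooled into a single dataset". The third adds a comparison: "We will compare statistical results using datasets with imputed values and the dataset that drops missing values". The text supplied does not give the number of imputations, the variables in the imputation model, or a rule for combining estimates and variances. One part of the document, between data management and the reference list, was not available for review.

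The rule covers all aims. For Aim 2 the plan is: "We will use mixed-effects linear regression analyses to examine intervention and time effects as well as intervention-by-time interactions". For Aim 3 it is "We will use mixed-effects linear regression analysis for continuous measures (VL, ARV adherence, and psychological symptoms", with no arm-by-time term named. The footnote to the measures table gives the schedule for in-person questionnaires and blood: "IQ occurs at 0 and 14 weeks. B occurs at 0 at 14 weeks". Cytokines, viral load, CES-D and GAD-7 therefore have one baseline and one follow-up value. The adherence VAS is an exception, described in Section 2.C as weekly. Section 3.A sets the expected loss: "Conservatively assuming 15% attrition in each arm, 42 participants will be in each arm".

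**The concern.** Multiple imputation gives valid standard errors because each completed dataset is analysed separately and the spread of the estimates between datasets is added to the variance. If the imputed datasets are first merged into one, by averaging the imputed values or by stacking the copies, that spread never reaches the standard error. The model then treats imputed values as if they had been observed, or counts each participant several times.

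The loss matters most for endpoints with a single follow-up visit, where a dropout loses all follow-up information. H2 and H3 rest on such endpoints, as does much of H4. The planned comparison with the dataset that drops missing values would also mislead: imputation would seem to gain precision that it does not give.

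**Working it through.** **Inputs from the plan (Section 3.A).** About 50 per arm and 15% attrition: 50 × 0.85 = 42.5, which the plan rounds to 42. So about 8 of 50 week-14 values per arm are imputed. The two-sided 5% level is stated for Aim 1 and assumed here for Aims 2-3. Correlations of 0.2 and 0.4 are the ends of the plan's ICC range.

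**Assumptions not in the plan.** Normal scores with SD 1, data missing completely at random, imputation from arm and baseline, M = 5 or 20 imputations, and an added correlation of 0.8.

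**Formulas, Aim 2 arm-by-time.** With two complete visits this term is the arm difference in change. Let ρ be the correlation between the visits.

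- Variance of change per person: v = 2(1 − ρ)
- Within-imputation variance: W = 2v/50
- Between-imputation variance (large-sample): B = 2 × (8/50)² × (1 − ρ²) × (1/42 + 1/8)
- Rubin total: T = W + (1 + 1/M)B
- Averaged dataset: an imputed participant's change has variance a = (1 − ρ)² + (1 − ρ²)/M instead of v, so the model reports A = (2/50) × (42v + 8a)/50
- The averaged dataset has the same point estimate as Rubin's rules, so its true variance is T and its false-positive rate is 2Φ(−1.96 √(A/T))

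**Numbers at ρ = 0.4, M = 5.**

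- v = 1.2 and W = 0.048
- B = 2 × 0.0256 × 0.84 × 0.1488 = 0.0064
- T = 0.048 + 1.2 × 0.0064 = 0.0557, SE 0.236
- a = 0.36 + 0.84/5 = 0.528
- A = 0.04 × (50.4 + 4.224)/50 = 0.0437, SE 0.209
- Ratio 0.886, false positives about 8.2%

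| ρ | M | SE, Rubin | SE, averaged | Ratio | False positives, averaged |
|---|---|---|---|---|---|
| 0.2 | 5 | 0.270 | 0.243 | 0.90 | 7.7% |
| 0.2 | 20 | 0.268 | 0.241 | 0.90 | 7.7% |
| 0.4 | 5 | 0.236 | 0.209 | 0.89 | 8.2% |
| 0.4 | 20 | 0.234 | 0.207 | 0.89 | 8.3% |
| 0.8 | 5 | 0.139 | 0.119 | 0.86 | 9.3% |
| 0.8 | 20 | 0.137 | 0.118 | 0.86 | 9.4% |

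Simulated null trials agree. At ρ = 0.4 (10,000 trials at M = 5, 4,000 at M = 20), the averaged dataset gave 8.2% and 8.1%, and Rubin's rules 4.7% and 5.0%. At ρ = 0.2 the averaged dataset gave 7.7% and 7.6%. Over all runs with correlations from 0.2 to 0.8, the averaged figure lay between about 7.5% and 10%.

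**Stacked copies, ρ = 0.4.** With participant ID kept but only a random intercept, the SE is 0.076 (M = 5) or 0.037 (M = 20), against 0.236 and 0.234. That gives 2Φ(−1.96 × 0.32) ≈ 53% and 2Φ(−1.96 × 0.16) ≈ 75% false positives. A fitted mixed model at M = 5 gave SE 0.076 and 51% (400 trials). With a person-level random slope the SE returns to 0.210.

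**Complete cases.** SE = √(2 × 1.2/42) = 0.239 at ρ = 0.4, with 4.6-5.9% simulated false positives. Set beside an averaged SE of 0.209, this suggests a precision gain of (0.239 − 0.209)/0.239 = 13%. Rubin's rules (0.236) show about 1%.

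**Aim 3, arm main effect over two visits.** The per-person variance is now (1 + ρ)/2, B is divided by 4, and an imputed participant's variance is ((1 + ρ)² + (1 − ρ²)/M)/4. At ρ = 0.4, M = 5:

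- T = 0.028 + 1.2 × 0.0016 = 0.0299, SE 0.173
- A = 0.04 × (42 × 0.7 + 8 × 0.532)/50 = 0.0269, SE 0.164
- Ratio 0.949, false positives 6.3%

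Simulation over ρ = 0.2-0.8 gave 5.0-6.8%.

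**Aim 1, simulated mixed-effects logistic test.** With dropout spread over follow-up, the averaged dataset gave 5.5-6.6% and Rubin's rules 4.6-5.5%, against 4.7-6.4% with no missing data. If every dropout left before the first rating, the averaged figure was 8.8-10.4% at M = 5 and 3.8-6.2% at M = 20.

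**Aim 1, responder definition.** Section 7.A also plans this: "We will compare the proportion of participants who achieve clinically significant change in pain at 14 weeks". Averaging scores before applying the 30% cut-off lowered a true 30% responder rate to between 25.6% and 29.2%. The lowest value arose when all dropouts left before the first rating.

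**The case against.** The strongest reply is that the sentence is loose wording. Its subject is results rather than records, and the next sentence keeps the imputed datasets in the plural; both fit the usual practice of pooling estimates. That may well be what was meant, and the documents cannot settle it. What remains is that the stated product is one dataset, and two analysts could follow the text and report different standard errors.

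Several other points stand:

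- The affected endpoints are secondary, and the plan calls its 15% attrition conservative.
- Normality is an assumption here. The plan does not state it for viral load and itself allows for non-normal cytokines.
- The comparison that drops missing values is near nominal. It does not, however, correct the standard errors from the imputed data.
- Which analysis is primary, the number of imputations and the imputation variables are missing detail rather than errors. The intention-to-treat statement and the order of the paragraph suggest that the imputed analysis leads.

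A reader might infer that a 50-75% false-positive rate follows from the plan. It does not. That needs stacking and a random intercept alone, and the plan specifies neither. A reader might also carry over the larger inflation of a baseline-adjusted week-14 comparison (about 9-10%; SE 0.17 averaged against 0.20 under Rubin's rules), but the plan does not specify that model for Aims 2-3.

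**Conclusion.** The point holds in a limited form. The rule names a single dataset as the product of pooling and gives no way to combine variances. If Rubin's rules were intended, this is a wording correction. Applied literally by averaging, it makes the Aim 2 arm-by-time standard error about 10-15% too small and gives about 7.5-10% false positives instead of 5%. This rests on 8 of 50 missing per arm, normal scores, data missing completely at random, M of 5 or 20, and correlations of 0.2-0.8.

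The documents do not support saying that standard errors are too small for all of Aims 2 and 3. Two-visit Aim 3 endpoints share the problem if arm-by-time is tested, but show only about 5-7% if the arm main effect is tested, and the plan does not say which. Nor do they support saying that the Aim 1 longitudinal test is compromised: it changes little if dropout is spread over follow-up.

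**What to change.** Replace the pooling sentence in Section 7.A with: *Each imputed dataset will be analysed separately with the planned model, and estimates and standard errors will be combined with Rubin's rules with small-sample degrees of freedom; the 0-10 BPI score will be imputed and the 30% responder indicator derived within each imputed dataset.* It would help to state at the same time the number of imputations, the imputation variables and which analysis is primary.

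No new data are needed, and standard software does this. The cost is wider, correct confidence intervals for Aims 2-3 (Aim 2 SE from about 0.21 to 0.235 at correlation 0.4) and a somewhat conservative week-14 responder test (2.1-4.6% false positives under Rubin's rules in simulation). If Rubin's rules were already intended, nothing changes but the text.

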The benefits of cannabis may be offset by its adverse events.²⁷ Cannabis is linked to psychological symptoms including anxiety, depression,²⁸ and psychotic symptoms.²⁹ In some studies, cannabis use is associated with poor ARV adherence and virologic failure;³⁰ in others, this is not the case.³¹ No studies have examined how THC/CBD content contributes to adverse events (psychological symptoms, poor ARV adherence, and virologic failure).

Our overarching goal is to test how medical cannabis use affects neuropathic pain, with particular attention to THC/CBD content and adverse events. We propose an observational cohort study of 100 PLWH with (a) neuropathic pain, (b) active certification for medical cannabis, and (c) intent of being dispensed soft-gel capsule products at a medical cannabis dispensary (including high THC: low CBD product and high CBD:low THC product). Over 14 weeks, participants will have 2 in-person visits and 15 phone-based questionnaires (one at baseline, and every week for 14 weeks). Data sources will be blood and urine samples, questionnaires, and medical and pharmacy records. The primary independent variable will be the type of soft-gel capsule product. The secondary independent variable will be reported cumulative THC and CBD dose. The primary outcome will be self-reported pain severity.³² Secondary outcomes will be pro-inflammatory cytokines (TNF α , IL-6), anti-inflammatory cytokines (IL-4, IL-10),¹⁵ psychological symptoms (symptoms of depression,³³ anxiety,³⁴ and psychosis³⁵), ARV adherence, and VL. Among PLWH with neuropathic pain, we will:

Aim 1: Examine how medical cannabis use affects self-reported pain. *H1:* The effect of medical cannabis use on self-reported pain-severity will differ by THC/CBD content.

Aim 2: Examine how medical cannabis use affects pro- and anti-inflammatory cytokines.

H2: Medical cannabis that has higher THC content will have greater reduction in pro-inflammatory cytokines (TNF α , IL-6). *H3:* Medical cannabis that has higher CBD content will have greater increase in anti-inflammatory cytokines (IL-4, IL-10).

Aim 3: Examine how medical cannabis use affects adverse events. *H4:* Participants who use high THC (vs. high CBD) cannabis products will have more psychological symptoms, poorer ARV adherence, and less suppressed VL.

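### The primary outcome is change in the BPI score, but the Aim 1 product comparison is specified and powered only as a 30% responder split

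*Combined protocol and SAP*

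**What the plan says.** Section 7.A, Aim 1, defines the primary outcome on the score scale: "The primary outcome will be change in BPI pain severity scale (ordinal variable, 0-10; measured at baseline and weekly for 14 weeks". The hypothesis, H1, is worded in terms of severity and names no metric: "The effect of medical cannabis use on self-reported pain-severity will differ by THC/CBD content".

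The next sentence of the Aim 1 text introduces a threshold: "A clinically significant change is 30% reduction in BPI pain severity scale". Two analyses of the product groups follow. The first is at a single visit: "We will compare the proportion of participants who achieve clinically significant change in pain at 14 weeks". The second is longitudinal: "We will use mixed-effects logistic regression to test the effect of study arm on pain relief across the course of the study". The text does not say whether pain relief in that model means the 30% responder, another binary cut, or the ordered score.

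Section 3.A takes the responder as the basis for sample size: "we based our power analysis on proportion of participants with clinically significant change in BPI pain severity scale (30% reduction) in each condition". Its headline result is: "We will have 84% power at a significance level of 5% (two-tailed test) to detect a 20% difference in proportion of participants", the contrast being the one "between high THC soft-gel capsules (40%) and high CBD (20%) soft gel capsules".

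Elsewhere in Section 7.A, Aim 2 (cytokines) and Aim 3 (viral load, adherence, psychological symptoms) are given mixed-effects linear models. Aim 4 has a mixed-effects model in which analgesia is the reduction in BPI severity score, and it calculates a standardised total effect of the exposures. That is a pooled analysis of THC and CBD dose.

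**The concern.** The outcome named as primary is the only main outcome for which no comparison of the product groups is planned on its own scale. Two things follow.

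First, the plan does not say which result decides H1. The candidates are the change in score, the week-14 responder proportion, and pain relief over the whole study. With the choice left open, it could be made after the data are seen.

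Second, cutting a 0-10 score at a 30% reduction discards information. With about 42 analysable participants per product group, it matters how much power that costs, and the answer depends on which of the planned tests is primary.

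**Working it through.** **Inputs.** From Section 3.A and Table 9: 42 per arm, two-sided 5%, responder rates 40% and 20%, ICC 0.2, 0.3 or 0.4. From Section 2.C: 14 weekly ratings after baseline. Not in the documents: the SD of BPI change, and the number of repeated ratings used in the power simulation (I take 14).

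**1. The plan's own figure.** Effective n per arm = 42 × 14 / (1 + 13 × ICC). At ICC 0.4 this is 588 / 6.2 = 94.8.

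Two-proportion power = Φ[(0.20 − 1.96·SE0) / SE1], with SE0 = √(2 × 0.3 × 0.7 / n) and SE1 = √((0.24 + 0.16) / n). At n = 94.8, SE0 = 0.0666 and SE1 = 0.0649, so power = Φ(1.07) = 0.858.

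| ICC | Table 9, 40% vs 20% | Recomputed | Table 9, 40% vs 15% | Recomputed |
|---|---|---|---|---|
| 0.2 | 0.97 | 0.979 | >0.99 | 0.999 |
| 0.3 | 0.91 | 0.927 | 0.99 | 0.993 |
| 0.4 | 0.84 | 0.858 | 0.96 | 0.976 |

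All six rows agree within 2 points (8 to 12 ratings fit as well). The stated power is therefore that of a repeated-measures responder analysis.

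**2. Implied difference on the score.** If change is normal with equal SD, d = z(0.80) − z(0.60) = 0.842 − 0.253 = 0.588.

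**3. Week 14 only, 42 per arm.**
- Responder: SE0 = √(0.42/42) = 0.100 and SE1 = √(0.40/42) = 0.0976. Power = Φ[(0.20 − 0.196)/0.0976] = Φ(0.04) = 0.516.
- Score: SE = √(2/42) = 0.218. Power = Φ(0.588/0.218 − 1.96) = Φ(0.736) = 0.769.
- For 80% power the responder test needs 82 per arm and the score 46.
- A simulated bounded 0-10 score (assumed baseline mean 5-6, baseline SD 1.5-2, change SD 1.5-2.5) gives 51-53% against 75-80%.

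**4. All 14 weeks, average difference.** Dichotomising a score lowers its ICC, so one ICC cannot serve both versions. I convert between them with the bivariate normal at the 40% and 20% cuts and average the two results.
- If 0.4 is the responder ICC, the score ICC is 0.59-0.64, mean 0.614. Effective n for the score is 588 / (1 + 13 × 0.614) = 65.4. Score power = Φ(0.588/√(2/65.4) − 1.96) = Φ(1.40) = 0.92, against 0.858 for the responder.
- If 0.4 is the score ICC, the responder ICC is about 0.24 and its effective n about 142. Responder power = 0.960. Score power at n = 94.8 is Φ(0.588/√(2/94.8) − 1.96) = Φ(2.09) = 0.982.

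| Stated ICC | Taken as responder ICC: responder / score | Taken as score ICC: responder / score |
|---|---|---|
| 0.4 | 86% / 92% | 96% / 98% |
| 0.3 | 93% / 96% | 98.6% / 99.5% |
| 0.2 | 97.9% / 99.2% | 99.8% / >99.9% |

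**The case against.** The best defence is that the responder endpoint was chosen openly. The 30% definition directly follows the primary-outcome sentence and can be read as its working form. Section 3.A calls the responder-based calculation the one for the primary analysis, and its 84% reproduces. H1 names no scale, so a responder comparison does address it. The week-14 shortfall comes largely from using one visit: the repeated-measures responder model already reaches about 86%. All of this stands, and it limits the point to a mismatch of specification with a moderate efficiency cost.

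A reader might go further and infer that the BPI score is never tested, or that the study cannot report a score difference. The documents do not support that. Aim 4 models reduction in the score and its relation to THC and CBD dose, and the weekly scores are collected, so a product difference can be estimated. What is missing is a prespecified comparison by product; an exploratory mediator analysis by dose does not supply one.

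A reader might also set 86% against 98% over the 14 weeks and conclude that much of the power is thrown away. That contrast gives the score and its dichotomised version the same ICC of 0.4, which cannot hold under the normal model used to derive d.

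Finally, the protocol calls the BPI scale ordinal, so the logistic model might be meant as an ordinal model of the score. The text neither says so nor excludes it. If that is the intention, a sentence would settle much of this.

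**Conclusion.** The point holds as a mismatch between the named primary outcome and the planned Aim 1 product comparison, with pain relief undefined and no statement of which result decides H1.

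The cost depends on the deciding test. If it is the week-14 proportion, the loss is large: about 25 points (52% against 77%), and Table 9 does not describe that test's power. If it is the longitudinal model, the loss is about 6 points or 2 points at ICC 0.4, depending on which ICC the plan means, and smaller at lower ICCs. It would be wrong to conclude that the stated 84% is an error: it fits the repeated-measures responder model.

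The score figures assume roughly normal change with equal SD in the two groups. The longitudinal ones also assume a constant difference over follow-up and exchangeable correlation. None of the figures models covariate adjustment.

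**What to change.** - Add to Aim 1 a longitudinal mixed model of weekly BPI severity with product, week, product-by-week and baseline BPI, alongside the covariate adjustment already planned. It may be linear, or ordinal in keeping with the protocol's label.
- Name one contrast in advance as the test of the primary outcome that decides H1. The average over follow-up is the one that the repeated-measures power supports; a week-14 contrast would need its own power statement.
- Define pain relief in the logistic model, and say whether the ICC in Section 3.A belongs to the responder or the score.
- Keep the 30% responder result beside it as the supportive analysis of clinical relevance.

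The cost is SAP wording and one more model on data already being collected. The downside is that a mean difference is less direct to interpret than a responder rate, which is the reason to keep both.
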